## SUMMARY

**Importance:** After a primary total knee arthroplasty (TKA), we anticipate that obese individuals are more likely to experience a of periprosthetic joint infection (PJI). Knowing the microbial profile in obese patients can potentially help in choosing the proper prophylactic measures for this group as well as tailoring the empirical antibiotics in relation to PJI in obese patients.

**Objective:** To compare incidence of PJI revisions within 2 years after TKA in obese vs non-obese OA patients. Secondarily: To compare microbial profiles of infections in these groups in two time windows: early ( $\leq 90$  days) vs late (91–730 days) and incidence of revisions due to all causes within 2 years. **Design and Setting:** We will include patients having primary knee arthroplasty using Danish national registers. Patients will be stratified into anthropometric groups, referred to as exposed and unexposed to obesity, based on their baseline Body Mass Index (BMI). Participants included in the analysis population will be followed up for 2 years, until first revision, death or migration whichever comes first.

**Participants:** We will include adult patients with available weight and height data with primary/idiopathic or secondary (due to meniscus or cruciate ligament lesion) OA who received primary TKA in the period from 2011-01-01 and 2021-02-28. Patients will be identified from the Danish knee arthroplasty register.

**Exposure and Comparator:** The cohort will be divided into obese (exposed), defined as body mass index (BMI)  $\geq 30$  kg/m $^2$ ; and non-obese (unexposed), defined as BMI  $< 30$  kg/m $^2$ .

**Main Outcomes and Measures:** The primary outcome will be revision due to prosthetic joint infection (PJI) within 730 days following TKA. Secondary endpoints will then be to examine revision due to all causes within 730 days following TKA and type of microbial infection between obese and non-obese in the first 90 days and the period from 91 days to 730 days following TKA.

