## Covariates

The cohort will be divided into two groups at baseline: obese, defined as  $\text{BMI} \geq 30 \text{ kg/m}^2$ , and non-obese, defined as  $\text{BMI} < 30 \text{ kg/m}^2$ . For descriptive purposes and adjusting, we will be using the following pre-TKA exposure covariates: age (years) at the time of TKA, sex (coded as female=1; male = 0), household income (at the year before KA, categorized into quartiles), highest completed education (at the year of KA, categorized into 3 categories: <11, 11 to 15, and >15 years). Comedication (at least one redeemed prescription 365 days earlier to index KA - 60 days for antibiotics): 1) Glucose-lowering due to the association between DM and surgical complications. 2) Antithrombotic medications and 3) NSAIDs because of the possible postoperative bleeding-related complications and 4) Antiresorptives due to the possible increased risk of revision. The last covariate to be included in matching and adjustment is Elixhauser Comorbidity Measure (ECM) (at the year of KA, categorized into 3: 0, 1-2 and  $\geq 3$ ), ECM is validated comorbidity scoring measure that has shown highest discriminative ability for the occurrence of all categories of postoperative adverse outcomes following orthopedic surgeries.

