## Sensitivity analyses

A sensitivity analysis will also be done to report PJI-likely revisions and the microbial profiles in these patients. PJI-likely revisions will be defined as revisions surgeries with at least one of the following: A) One single intraoperatively obtained positive culture obtained from the revision surgery (aspiration fluid OR tissue biopsy) regardless of the microorganism. B) One single positive culture obtained from aspiration of synovial fluid regardless of microorganism. If we do not find a difference between obese and non-obese, we will run a sensitivity analysis where we compare morbidly obese patients ( $BMI \geq 40 \text{ kg/m}^2$ ) with other patients ( $BMI < 40 \text{ kg/m}^2$ ). If the primary analysis showed a difference between obese and non-obese, a sensitivity analysis comparing morbidly obese ( $BMI \geq 40 \text{ kg/m}^2$ ) with non-morbidly obese ( $BMI 30-40 \text{ kg/m}^2$ ) will be done.

**Sensitivity analysis table 1:** Incidence for Periprosthetic joint infection-likely (PJI) revision at 2 years in obese and non-obese patients with the relative risk (RR) and an unadjusted and adjusted analyses of the Hazard Ratios (HR) between the 2 groups

|                           | Obese   | Non-Obese | HR [95% CI*]  |
|---------------------------|---------|-----------|---------------|
| Crude analyses:    |         |           |               |
| N                         | xx      | xx        |               |
| PJI-likely, no. (%)       | xx (xx) | xx (xx)   | xx [xx to xx] |
| Adjusted analyses: |         |           |               |
| N                         | xx      | xx        |               |
| PJI-likely, no. (%)       | xx (xx) | xx (xx)   | xx [xx to xx] |

\*CI: Confidence Interval

**Sensitivity analysis table 2:** Prosthetic joint infection-likely (PJI-likely) within the first 90 days and in 91 days-2 years postoperatively stratified by the type of infection

|   | Obese   | Non-Obese | Absolute Risk difference [95% CI*] |
|---|---------|-----------|------------------------------------|
| N   | xx      | xx        |                                    |
| PJI-likely, 90 days, no. (%)           | xx (xx) | xx (xx)   | xx [xx to xx]                      |
| Staphylococcus aureus, no. (%)                | xx (xx) | xx (xx)   | xx [xx to xx]                      |
| Coagulase-negative staphylococci, no. (%)     | xx (xx) | xx (xx)   | xx [xx to xx]                      |

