| Other gram-positive, no. (%)                  | xx (xx) | xx (xx)   | xx [xx to xx]                      |
| Gram-negative, no. (%)                        | xx (xx) | xx (xx)   | xx [xx to xx]                      |
| Anaerobes, no. (%)                            | xx (xx) | xx (xx)   | xx [xx to xx]                      |
| Fungal, no. (%)                               | xx (xx) | xx (xx)   | xx [xx to xx]                      |
| Mycoplasma, no. (%)                           | xx (xx) | xx (xx)   | xx [xx to xx]                      |
| Multibacterial, no. (%)                       | xx (xx) | xx (xx)   | xx [xx to xx]                      |
| PJI-likely, 91 days - 2 years, no. (%) | xx (xx) | xx (xx)   | xx [xx to xx]                      |
| Staphylococcus aureus, no. (%)                | xx (xx) | xx (xx)   | xx [xx to xx]                      |
| Coagulase-negative staphylococci, no. (%)     | xx (xx) | xx (xx)   | xx [xx to xx]                      |
| Other gram-positive, no. (%)                  | xx (xx) | xx (xx)   | xx [xx to xx]                      |
| Gram-negative, no. (%)                        | xx (xx) | xx (xx)   | xx [xx to xx]                      |
| Anaerobes, no. (%)                            | xx (xx) | xx (xx)   | xx [xx to xx]                      |
| Fungal, no. (%)                               | xx (xx) | xx (xx)   | xx [xx to xx]                      |
| Mycoplasma, no. (%)                           | xx (xx) | xx (xx)   | xx [xx to xx]                      |
| Multibacterial, no. (%)                       | xx (xx) | xx (xx)   | xx [xx to xx]                      |

\*The 95% confidence intervals (CI) will not be adjusted for multiplicity and should not be used in place of hypothesis testing.

**Sensitivity analysis table 3:** Incidence for Periprosthetic joint infection (PJI) and all cause revision at 2 years in morbidly obese and non-morbid patients with an unadjusted and adjusted analyses of the Hazard Ratios (HR) between the 2 groups

|                                     | Morbidly-Obese | Non-morbid | HR [95% CI*]  |
|-------------------------------------|----------------|------------|---------------|
| Crude analyses:              |                |            |               |
| N                                   | xx             | xx         |               |
| PJI, no. (%)                        | xx (xx)        | xx (xx)    | xx [xx to xx] |

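### BMI 40 or more is never compared on its own with the study's unexposed group (BMI below 30), and its reference group changes with the primary result

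*Combined protocol and SAP*

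**What the plan says.** The Covariates section sets up a binary exposure: "The cohort will be divided into two groups at baseline: obese, defined as" BMI 30 or more, with everyone below 30 as non-obese. The Summary calls the group below 30 unexposed. Patients with BMI 40 or more are therefore part of the exposed group.

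The Sensitivity analyses section then plans one of two morbid-obesity comparisons:

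- "If we do not find a difference between obese and non-obese, we will run a sensitivity analysis where we compare morbidly obese patients" with all other patients, meaning BMI below 40.
- "If the primary analysis showed a difference between obese and non-obese, a sensitivity analysis comparing morbidly obese" with non-morbidly obese patients, meaning BMI 30–40, will be done.

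Sensitivity table 3 is to report PJI and "all cause revision at 2 years in morbidly obese and non-morbid patients". Sensitivity table 4 does the same for the microbial profiles. Both shells have two group columns, morbidly obese and non-morbid, and no column for BMI below 30. The same non-morbid label has to serve both possible reference groups.

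**The concern.** One reference group (below 40) mixes unexposed patients with patients who are exposed under the study's own definition. The other (30–40) consists wholly of exposed patients. Patients with BMI 40 or more meet the group below 30 only as part of the pooled obese group in the primary analysis.

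Two things are at stake. First, a reader who wants to know how PJI risk at BMI 40 or more compares with that of non-obese patients will not find an adjusted answer. Crude risks could be pieced together from the counts in Table 2 and sensitivity table 3. The weighted hazard ratio and its interval could not, because the propensity weights would have been estimated for other contrasts. Second, the meaning of the reported morbid-obesity hazard ratio depends on which way the primary result falls.

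The protocol's premise makes this more than a matter of labels. The Summary anticipates more PJI in obese patients, and the Introduction names rising BMI as the risk factor most consistently linked to PJI. If BMI 30–40 carries more risk than BMI below 30, a reference group containing those patients gives a smaller ratio than the unexposed group would.

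**Working it through.** **The plan's own figure.** Statistical Methods takes a 2-year PJI incidence of about 1%, treats a 50% increase as clinically relevant, and equates this with a hazard ratio of 1.5. Check: ln(1 − 0.015) / ln(1 − 0.010) = 1.504. The figure is reproduced. The documents give no figure for the morbid-obesity comparison.

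**Inputs.** The group definitions come from the Summary, Covariates and Sensitivity analyses sections. Everything else is assumed, because the documents state no BMI shares and no risks by BMI class:

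- HRm: hazard ratio of BMI 40 or more against below 30.
- HRo: hazard ratio of BMI 30–40 against below 30.
- a, b, c: cohort shares of BMI below 30, 30–40, and 40 or more. Three sets were tried: 60/36/4, 55/40/5 and 50/40/10%.

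**Formulas** (rare events, so hazards are averaged by share):

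- Primary contrast, obese against non-obese: (b × HRo + c × HRm) / (b + c)
- 40 or more against below 40: HRm / [(a + b × HRo) / (a + b)]
- 40 or more against 30–40: HRm / HRo

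**Results for HRm = 2.0 and shares 55/40/5%.** Percentages show the departure from 2.0; they do not depend on HRm.

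| HRo | Obese vs non-obese | 40+ vs below 40 | 40+ vs 30–40 |
|---|---|---|---|
| 0.9 | 1.02 | 2.09 (+4%) | 2.22 (+11%) |
| 1.0 | 1.11 | 2.00 (0%) | 2.00 (0%) |
| 1.1 | 1.20 | 1.92 (−4%) | 1.82 (−9%) |
| 1.25 | 1.33 | 1.81 (−10%) | 1.60 (−20%) |
| 1.5 | 1.56 | 1.65 (−17%) | 1.33 (−33%) |

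Worked row, HRo = 1.25: (0.55 + 0.40 × 1.25) / 0.95 = 1.105, and 2.0 / 1.105 = 1.81; 2.0 / 1.25 = 1.60.

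Over the three sets of shares, the below-40 column moves only slightly: about −4% at HRo 1.1, −9 to −10% at 1.25, −16 to −18% at 1.5, and +4 to +5% at 0.9. The 30–40 column does not depend on the shares.

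**Effect of the trigger.** The below-40 comparison runs only when the primary contrast shows no difference, so its rows are not equally plausible. Fix the primary hazard ratio at exactly 1.0 with HRm = 2.0 and shares 55/40/5%. Then 0.40 × HRo + 0.05 × 2.0 = 0.45, so HRo = 0.875, and 2.0 / [(0.55 + 0.35) / 0.95] = 2.11. Over the three sets of shares, HRo is 0.75–0.89 and the ratio against below 40 is 2.09–2.25, larger than 2.0. With the primary hazard ratio at 1.2, it is 1.92–2.00. In the table, a shortfall of about 10% goes with a primary hazard ratio of about 1.33. That result would have to be classed as no difference because the estimate was imprecise.

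**The case against.** The strongest reply has four parts.

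1. **Understatement is not certain.** A reader might infer that the plan is bound to understate the effect of morbid obesity. The documents do not support this. The planned ratios are smaller only if BMI 30–40 carries more risk than BMI below 30. At HRo = 1.0 nothing changes, and below 1.0 the direction reverses. In the below-40 branch the trigger itself keeps the dilution small. This part stands.

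2. **BMI 40 or more against 30–40 is a valid contrast.** It asks whether there is added risk within the obese, and the text labels the reference group openly. It misleads only if read as a contrast with non-obese patients. This stands too, and is a reason to keep the contrast. It does not supply the missing one.

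3. **The 1.5 margin does not show harm.** A reader might infer that someone holding the planned ratios against 1.5 would wrongly conclude that morbid obesity carries no important excess. With assumed 2-year risks of 1.0%, 1.3% and 1.7%, for instance, the ratio against 30–40 is 1.7 / 1.3 = 1.31, while against below 30 it is 1.70. But the rule in Statistical Methods uses the upper 95% confidence bound, not the point estimate, and the section warns that a non-significant result does not show absence of difference. For an observed 1.31 to have an upper bound below 1.5, the standard error of the log ratio must be under ln(1.5 / 1.3077) / 1.96 = 0.070. With assumed shares of 57/40/3 to 50/45/5%, that takes about 224–234 events among patients with BMI 40 or more, and so a cohort of roughly 275,000–440,000. Nor does the plan extend the margin to these sensitivity contrasts.

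4. **Morbid obesity is not a listed objective,** and the primary contrast is unaffected. This is correct and limits the weight of the point. Still, the plan has chosen to analyse morbid obesity, and its own unexposed group is the natural reference.

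**Conclusion.** The point holds as an omission. The plan gives no estimate of BMI 40 or more against its own unexposed group, and the reference group it does use depends on the primary result. This follows from the text and needs no assumption.

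The numerical consequence is conditional. If risk rises with BMI, the planned hazard ratio in the 30–40 branch is smaller than the ratio against below 30 by about 9% to 33%, for assumed HRo of 1.1 to 1.5. This is also the branch that the protocol's expected result would trigger. In the below-40 branch the gap is a few percent or reversed when the primary hazard ratio is near 1. It reaches about 10% or more only if the finding of no difference reflects imprecision; the section does not say how a difference is to be judged. All these sizes rest on assumed shares and hazard ratios.

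The primary comparison of obese with non-obese patients is not affected. This is an inexpensive improvement to a sensitivity analysis.

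**What to change.** In the Sensitivity analyses section and in sensitivity tables 3 and 4, before the data are analysed:

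- Prespecify a three-level exposure (BMI below 30, 30 to below 40, 40 or more) with BMI below 30 as reference, and report it whatever the primary result.
- Estimate the propensity weights for these three groups instead of reusing the binary weights.
- Give sensitivity tables 3 and 4 one column per BMI group, in place of the non-morbid label.
- Keep BMI 40 or more against 30 to below 40 as a supporting contrast, labelled as added risk within the obese.

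No new data are needed. The cost is one more model and a wide interval for the small top group. As an illustration, assume 30,000 patients, shares of 55/40/5% and risks of 1.0%, 1.3% and 2.0%, which give 165, 156 and 30 events. Ignoring weighting, the standard error of the log hazard ratio against below 30 is √(1/30 + 1/165) = 0.198, so an estimate of 2.0 would have a 95% interval of about 1.36 to 2.95. The planned contrasts are hardly more precise: √(1/30 + 1/321) = 0.191 against below 40 and √(1/30 + 1/156) = 0.199 against 30–40. The width comes from the few events at BMI 40 or more, and all of these are kept.

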## HEALTH RESEARCH ETHICS AND GENERAL CONSIDERATIONS

### Funding

Section for Biostatistics and Evidence-Based Research, the Parker Institute, Bispebjerg and Frederiksberg Hospital is supported by a core grant from the Oak Foundation (OCAY-18-774-OFIL). [name] is supported by a grant from Karen Elise Jensens Fond. The supporting institutions had no role in study design or writing of this protocol.

### Conflict of interest

All will be disclosed.

### Disclaimers

The views expressed in the submitted protocol are the authors' own and not an official position of the institution or funder.

### Ethics

In Denmark, the Act on Processing of Personal Data does not require ethical permission or obtained consent for anonymised retrospective register studies. The Danish Data Protection Agency has approved the study with nr p-2023-14433.

